### **7.3. Participant Population for Analysis**

Data from protocol-compliant participants will be used for analysis.

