#### 3.2 Primary Study Endpoints

CONFIDENTIAL

This material is the property of the University of Pennsylvania. Do not disclose or use except as authorized in writing by the study sponsor

- Primary smoking status will be assessed using the Timeline Follow-back method (165) and by using carbon monoxide (CO) concentration to biochemically verify the self-report. Participants will be considered to be abstinent if they self-report abstinence (not even a puff

of a cigarette) for  $\geq 7$  days prior to the assessment after 10 weeks of treatment and at 24 weeks post-TQD and have a CO  $\leq 10$  ppm at that time (166-167). As per convention, participants are assumed to be smoking if they self-report to be smoking at the time point, cannot be reached to provide data at the time point, fail to provide a breath sample at the time point, or provide a breath sample at the time point that has a CO concentration  $> 10$  ppm (166).

- For adverse effects, our primary outcome will be the frequency of moderate or severe side effects from a checklist of bupropion-related side effects (derived from completed bupropion studies), as well as those elicited with open-ended questions, through regular obstetrics visits, and assessments triggered by any pregnancy-related complication. Adverse effects will be systematically assessed by study personnel at 5 time points over the course of the 10-week study and can trigger dose reductions or suspension of medication.
- Birth outcomes obtained from labor and delivery records (permission for which will be included in the informed consent form) will include gestational age, overall and spontaneous preterm birth (i.e., at less than 37 weeks), infant birth weight, whether small for gestational age (i.e.,  $< 10^{\text{th}}$  percentile birth weight for gestational age as determined by the Alexander curve), head circumference, Apgar scores, and NICU admissions. Obstetric complications will include type of delivery and delivery and postpartum complications.

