at the UPenn site will enter the variables into the randomization program, which will assign a randomization group to the participant; 3) the designated study staff member will fax the participant's randomization group to IDS, which will assign a kit number to the participant and fax the kit assignment to the research coordinator; 4) the research nurse or physician will dispense medication to the participant and complete and sign the IDS prescription form included in the starter kit; 5) The research coordinator will fax the completed form to IDS. The medication will be dispensed using the above dosing schedule. To maintain double-blind conditions, study staff responsible for randomization will not be involved in the recruitment of participants, study visits, or data collection. IDS will provide each study site a supply of starter kits to use for initial study medication dispensing.

Study drug for subsequent visits will be ordered by the research coordinator using the "Research Pharmacy Schedule" form, a copy of which will be retained in the participant's research file. The study drug will be ordered at Baseline Visit B for Weeks 2-5 and Target Quit Day Visit C for Weeks 6-10. The study drug will be picked up at IDS and brought to the study visit. If the participant is unable to attend the scheduled study visit the study drug will be stored at the Treatment Research Center in the Medication Room. Study drug will be dispensed at three time points during the study: Baseline (Visit B: 1 week of medication), Target Quit Date (Visit C: 4 weeks of medication), and Week 5 (Visit E: 5 weeks of medication). The initial dispensing will be done directly by the research nurse or physician, who will ensure that the patient understands the medication regimen. Study medication will be dispensed by the research nurse, physician, or research coordinator (trained and supervised by the nurse or physician), who will assess each participant for study medication AEs, documenting and reporting them as required. Participants with severe psychological symptoms or determined to be inappropriate for the study by an investigator will be withdrawn from the study. A study nurse or physician will follow participants withdrawn completely from treatment until they are referred for appropriate clinical care. For research purposes, and with the participant's continued approval, we will collect data at all subsequent time points until the 24 weeks post-TQD visit.

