### **6.11 Early Termination Visit (Approximately 30 minutes, in-person or divided between in-person and telephone sessions)**

Participants who discontinue treatment prematurely will be asked to complete an end-of-treatment evaluation and all scheduled assessments to facilitate intention-to-treat (ITT) analyses. Participants will be informed of these procedures prior to study enrollment. Participants who terminate participation in the treatment prior to Week 10 will also be asked to complete the scheduled end-of-treatment (Week 10) procedures. For this and any other visit that cannot be completed in-person, assessments will be conducted by telephone.

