### **6.12 Other Study Procedures and Considerations**

Screening and baseline visits cannot occur on the same day. The maximum time permitted to elapse between completion of the screening visit and completion of the baseline visit is 30 days. Every effort will be made to complete visits within a 3-day window before or after the date scheduled for the visit as shown in Table 2. However, because the analysis will be intent-to-treat, we will reasonably accommodate subjects' time constraints by extending the window as needed to complete all study visits. During the week prior to each of the visits (B through J), a reminder call will be made to the participant concerning the next scheduled visit. At the reminder call for Visit H (24 weeks post-TQD) the participant will be asked whether she had smoked at all during the previous week. Visit H will be held plus or minus 28 days from the scheduled 24 week post-TQD. This large window accommodates changes in delivery dates and also allows the visit to coincide with the inpatient delivery or the 6-week post-partum office visit, an important convenience for a new mother. If she acknowledges having smoked, an in-person visit is not required but may be held. If she reports no smoking, an in-person visit will be conducted to verify self-report using breath CO measurement. Because breath CO is a non-invasive and simple test, as well as an important outcome measure, we will collect a breath CO reading at all in-person opportunities when feasible, including at time of delivery and at the time of the 6-week post-partum visit. If the blood draw is unsuccessful at the baseline visit, a second attempt will be made at the Week 5 visit. If the second draw is successful, the baseline tubes will also be drawn (for all baseline tests if the participant is still smoking or for DNA only if the participant is no longer smoking). If the second draw is not successful, we will collect DNA from the patient's saliva using the Oragene Discover Kit (PD-LB-00191).

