## **7.2. Statistical Analyses**

[name] will oversee analyses, which will be conducted using Stata, SAS, or R-Language software. Preliminary analyses will assess sample characteristics (e.g., dependence, race) by treatment using t-test or contingency table methods. These variables will also be examined for their relationship to completion of outcome assessments. Variables related to treatment arm or completion of follow ups will be included as covariates in analyses of study aims. Compliance measures will be evaluated across treatment arms, and controlled for in primary analyses. We will examine the correlation between self-report and pill count data and week-5 bupropion plasma levels. We will use intent-to-treat as the primary method to evaluate study aims.

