### **7.2.1. Missing Data:**

We will examine whether the rate of missing data, primarily our smoking cessation outcome data, is related to a range of potential variables, including treatment arm allocation, and demographic and smoking-related variables. Standard bivariate statistical methods will be used to identify correlates of missing data. Variables associated with the rate of missing data ( $p < 0.05$ ) will be included as covariates in the analyses of aims. Items missing at random from assessments will be imputed prior to calculating final scores using conditional means, estimated with an iterated version of Buck's method (173). We will aim to avoid dropout and missed sessions by keeping participants connected to the trial and motivated to complete measures. In our clinical trials, close monitoring of participants and the use of incentives to offset travel costs have resulted in adherence and retention rates >80% (52). Primary analyses will assume that all participants for whom smoking outcome data are unavailable are smokers (intent-to-treat), which is conventional in smoking cessation research. Because this assumption can attenuate the differences between study groups in quit rates, we will also conduct a "completers-only" analysis, as done previously (174).

CONFIDENTIAL

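### Section 7.3 restricts analysis to protocol-compliant women, and section 7.2 adjusts the primary analyses for compliance; neither fits the plan's intent-to-treat primary analysis

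*Combined protocol and SAP*

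**What the plan says.** Section 7.3, Participant Population for Analysis, consists of one sentence: "Data from protocol-compliant participants will be used for analysis". It names no hypothesis and does not describe itself as secondary.

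Elsewhere the plan says the opposite:

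- Section 7.2: "We will use intent-to-treat as the primary method to evaluate study aims". The Study Summary agrees.
- Section 7.2.1: "Primary analyses will assume that all participants for whom smoking outcome data are unavailable are smokers (intent-to-treat"). It adds a completers-only analysis as a supplement.
- Section 6.11 asks women who stop treatment early to complete "all scheduled assessments to facilitate intention-to-treat (ITT) analyses".
- Section 6.12 justifies flexible visit windows: "because the analysis will be intent-to-treat, we will reasonably accommodate".
- Section 5.3, on women withdrawn from treatment who agree to go on: "we will collect data at all subsequent time points until the 24 weeks post-TQD visit".

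On covariates, section 7.2 and the Study Summary both state: "Compliance measures will be evaluated across treatment arms, and controlled for in primary analyses". Section 3.2 says adverse effects "can trigger dose reductions or suspension of medication". Section 10.1 (Measures for Participant Safety) says adverse events will serve as a covariate as well as an outcome, without naming the model.

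**The concern.** There are two defects of different kinds.

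The first is a conflict over who is analysed. A compliant-only set can drop women whom section 7.2.1 keeps and counts as smokers. An analyst following 7.3 and one following 7.2 could report different primary results for H1. Without a rule for compliance fixed in advance, there is also room to choose after the data are seen. Because 7.3 is unrestricted, it reaches the safety (H2) and birth-weight (H3) analyses too.

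The second is a conflict over what is estimated. The compliance covariate removes nobody. But compliance is observed after randomisation, and treatment may change it. If it is related to both arm and quitting, the adjusted odds ratio is not the effect of assignment, which is what an intent-to-treat analysis is meant to give.

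**Working it through.** **Which population the sample size assumes.** Inputs: quit rates 21.2% and 35.9% (section 7.1.1), 180 per arm (section 5.3), two-sided alpha 0.05 (section 7.1).

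- Difference: 0.359 − 0.212 = 0.147. Mean rate: 0.2855.
- Pooled standard error: √(2 × 0.2855 × 0.7145 / 180) = 0.0476.
- Unpooled standard error: √(0.212 × 0.788 / 180 + 0.359 × 0.641 / 180) = 0.0470.
- Power, pooled test: Φ[(0.147 − 1.96 × 0.0476) / 0.0470] = Φ(1.143) = 87.3%.
- Power, unpooled test: Φ(0.147 / 0.0470 − 1.96) = Φ(1.169) = 87.9%.

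The stated 88% is reproduced with every randomised woman counted and nothing taken off for non-compliance.

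**Whether a compliant-only set would lose power.** No loss is claimed, because the sign depends on the quit rates assumed in compliers. With 80% compliance assumed (144 per arm), power is 79% if compliers quit at the same 21.2% and 35.9%. It is 91% to 93% if those rates hold for all randomised women and non-compliers in both arms quit at a common rate between 0% and 21.2%.

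**How far the estimate can move.** The documents give none of the inputs needed apart from the placebo quit rate, so the following are assumptions: no drug effect, 21.2% quitting in both arms, 95% of quitters compliant in both arms, and 76% of placebo non-quitters compliant. Only compliance among bupropion non-quitters is varied. At 56%:

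- Placebo compliers: 0.212 × 0.95 + 0.788 × 0.76 = 0.2014 + 0.5989 = 0.800. Quit rate among them: 0.2014 / 0.800 = 25.2%.
- Bupropion compliers: 0.2014 + 0.788 × 0.56 = 0.643. Quit rate among them: 0.2014 / 0.643 = 31.3%.
- Compliant-only odds ratio: quitters contribute equally in the two arms, so it reduces to 0.76 / 0.56 = 1.36.
- Compliance-adjusted odds ratio: a logistic model with arm and compliance, fitted to the expected counts for all 360 women, gives 1.28.

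| Compliance, bupropion non-quitters | Compliant-only OR | Compliance-adjusted OR, all 360 |
|---|---|---|
| 76% (same as placebo) | 1.00 | 1.00 |
| 71% | 1.07 | 1.05 |
| 66% | 1.15 | 1.12 |
| 61% | 1.25 | 1.19 |
| 56% | 1.36 | 1.28 |
| Arms swapped (placebo 56%, bupropion 76%) | 0.74 | 0.78 |

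The true odds ratio is 1.00 in every row. The bias runs either way and vanishes in this example when compliance is the same in both arms.

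**The case against.** The strongest reply is that the intended H1 analysis is fairly clear. Several sections say intent-to-treat, section 7.2.1 in effect sets the primary H1 population by counting missing as smoking, and one undefined sentence in 7.3 is outnumbered. That makes the likely intention plain, but 7.3 is still the section headed as the analysis population and it says something else. The completers-only analysis does not bridge the gap, since it turns on available outcome data rather than compliance.

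The covariate, it can be said, excludes nobody and so does not contradict intent-to-treat in the same sense. That is right, and it is why the two defects are treated separately here. Section 7.2.2 gives only baseline variables as examples of covariates for the H1 model, but the list is illustrative and does not displace the explicit statement in 7.2.

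On definition, section 4.4.1 withdraws women who fail to adhere to protocol requirements, which is the nearest the text comes to a meaning for protocol-compliant. Section 5.5, on compliance, is in the contents but its text is absent from this copy. No weight is put on the missing definition: supplying one would leave the conflict in place.

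On mechanism, a dose reduction or suspension that the protocol permits need not count as non-compliance. Section 7.1.1 reports 45% versus 47% free of moderate-to-severe adverse events in the investigators' earlier bupropion study, which suggests little difference between arms by this route. No figure in the documents supports the 16-point compliance gap behind the 1.36. These points stand, and they are why the odds ratios are an illustration and not a forecast.

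Lastly, H2 is an equivalence test, for which an all-randomised analysis is not automatically conservative. That stands too: the H2 population needs its own statement.

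**Conclusion.** The concern holds. The conflict between section 7.3 and the intent-to-treat primary analysis is in the text and depends on no calculation. The compliance covariate is a separate fault: it changes what the primary odds ratio estimates even when all 360 women are analysed. The power check shows only that the sample size was set for everyone randomised. The size and direction of any bias cannot be derived from the documents. Under the assumptions shown, it spans 0.74 to 1.36 for a compliant-only analysis and 0.78 to 1.28 for an adjusted one, against a true value of 1.00, and is nil in the example when compliance does not differ by arm. This should be corrected before unblinding. The adverse-event covariate in section 10.1 is an ambiguity to clear up, not a demonstrated error.

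**What to change.** Core changes:

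1. Replace section 7.3 with wording such as: *All randomised participants, analysed as randomised, form the primary population for H1, with missing smoking status counted as smoking. Protocol-compliant analyses, with compliance defined before unblinding, are sensitivity analyses.*
2. In section 7.2 and the Study Summary, delete the clause that controls for compliance in the primary analyses, and describe compliance by arm instead.
3. Limit covariates in the primary efficacy models to baseline variables.

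Clarifications to make at the same time, because 7.3 now covers every hypothesis:

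- For H2, state before unblinding whether the population is all randomised women or all who received study drug.
- For H3, use all randomised women regardless of compliance, report missing birth weights by arm, and fix the handling rule before unblinding.
- In section 10.1, say that adverse events are not a covariate in the primary efficacy models.

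The cost is protocol and SAP wording. Outcome collection after treatment stops is already planned in sections 5.3, 6.11 and 6.12, so no new visits or data are needed, and the compliance-based analyses can still be reported under their own label.

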## **8. Safety and Adverse Events**

### **8.1. Definitions**

#### **Adverse Event - Maternal**

An **adverse event** (AE) is any symptom, sign, illness or experience that develops or worsens in severity during the course of the study. Intercurrent illnesses or injuries should be regarded as adverse events. Abnormal results of diagnostic procedures are considered to be adverse events if the abnormality:

- results in study withdrawal
- is associated with a serious adverse event
- is associated with clinical signs or symptoms
- leads to additional treatment or to further diagnostic tests
- is considered by the investigator to be of clinical significance

CONFIDENTIAL

### **Serious Adverse Event - Maternal**

Adverse events are classified as serious or non-serious. A **serious adverse event** is any AE that is:

- fatal
- life-threatening
- requires or prolongs hospital stay
- results in persistent or significant disability or incapacity
- an important medical event

Important medical events are those that may not be immediately life threatening, but are clearly of major clinical significance. They may jeopardize the participant wellbeing, and may require intervention to prevent one of the other serious outcomes noted above. For example, drug overdose or abuse, a seizure that did not result in inpatient hospitalization, or intensive treatment of bronchospasm in an emergency department would typically be considered serious.

All adverse events that do not meet any of the criteria for serious should be regarded as **non-serious adverse events**.

### **Adverse Event – Neonate**

An **adverse event** (AE) is any symptom, sign, illness or experience that develops or worsens in severity during gestation or at birth. Intercurrent illnesses or injuries should be regarded as adverse events. Abnormal results of diagnostic procedures are considered to be adverse events if the abnormality:

- results in study withdrawal
- is associated with a serious adverse event
- is associated with clinical signs or symptoms
- leads to additional treatment or to further diagnostic tests
- is considered by the investigator to be of clinical significance
- results in prolonged hospitalization in the NICU due to neonatal abstinence syndrome (expected for babies exposed to methadone or buprenorphine) or premature birth (expected for babies whose mothers' smoke)
- conditions associated with premature birth, such as patent ductus arteriosus

### **Serious Adverse Event – Neonate**

Adverse events are classified as serious or non-serious. A **serious adverse event** is any AE develops or worsens in severity during gestation or at birth that is:

- fatal
- life-threatening
- requires or prolongs hospital stay in the NICU (except for neonatal abstinence syndrome)
- results in persistent or significant disability or incapacity
- results in a congenital anomaly or birth defect
- results in any unexpected condition not explained by gestational history

Important medical events are those that may not be immediately life threatening, but are clearly of major clinical significance. They may jeopardize the participant wellbeing, and may require intervention to prevent one of the other serious outcomes noted above. For example, drug overdose or abuse, a seizure that did not result in inpatient hospitalization, or intensive treatment of bronchospasm in an emergency department would typically be considered serious.

CONFIDENTIAL

### **Adverse Event Reporting Period**

The study period during which adverse events must be reported will be defined as the period from the initiation of any study procedures to the end of the last assessment.

### **Pre-existing Condition**

A pre-existing condition is one that is present at the start of the study. A pre-existing condition should be recorded as an adverse event if the frequency, intensity, or the character of the condition worsens during the study period.

At screening, any clinically significant abnormality or disorder should be recorded as a pre-existing condition. At the end of the study, any new clinically significant findings/abnormalities or disorder that meets the definition of an adverse event must also be recorded and documented as an adverse event.

### **Post-study Adverse Event**

All unresolved adverse events will be followed by the investigator until the events are resolved, the participant is lost to follow-up, or the adverse event is otherwise explained. At the last scheduled visit, the investigator should instruct each participant to report any subsequent event(s) that the participant, or the participant's personal physician, believes might reasonably be related to participation in this study. The investigator should notify the IRB of any adverse event occurring at any time after a participant has discontinued or terminated study participation that may reasonably be related to this study. The IRB will also be notified if the investigator should become aware of the development of cancer or of a congenital anomaly in a subsequently conceived offspring of a participant that has participated in this study.

### **Hospitalization, Prolonged Hospitalization or Surgery**

Any adverse event that results in hospitalization or prolonged hospitalization should be documented and reported as a serious adverse event unless specifically instructed otherwise in this protocol. Any condition responsible for surgery should be documented as an adverse event if the condition meets the criteria for an adverse event.

Neither the condition, hospitalization, prolonged hospitalization, nor surgery are reported as an adverse event in the following circumstances:

- Hospitalization or prolonged hospitalization for diagnostic or elective surgical procedures for a preexisting condition. Surgery should **not** be reported as an outcome of an adverse event if the purpose of the surgery was elective or diagnostic and the outcome was uneventful.
- Hospitalization or prolonged hospitalization required to allow efficacy measurement for the study.
- Hospitalization or prolonged hospitalization for therapy of the target disease of the study, unless it is a worsening or increase in frequency of hospital admissions as judged by the clinical investigator. Thus, hospitalization for normal childbirth is not considered an adverse event.

